9.4 Screening Failures and Withdrawals

9.4.1 Screening failures

Screening failures will be all patients who have been enrolled in the study (i.e. ICF signed), but discontinue the study before the first IMP intake at visit A1 due to whatever reason (withdrawn consent, do not fulfil criteria, by decision of investigator, etc.).

One additional attempt at screening may be permitted within 4 weeks.

In addition to their records of performed assessments, screening failures have to be documented on the termination page of the electronic case report form (eCRF).

9.4.2 Withdrawals

Patients who have been enrolled and, for whatever reason, discontinue the study after first IMP intake at visit A1 are classified as withdrawals. Patients may withdraw from the study at any time, either on their own request or at the discretion of the investigator.

Reasons for withdrawal must be documented carefully in the patient's medical records and in the eCRF. Investigators must attempt to contact patients who fail to attend scheduled visits by telephone, letter, visit, etc., to exclude the possibility of an AE being the cause. Should this be the case, the AE must be documented, reported and followed up as described in Section 12. Attempts to contact the patient must be documented in the patient's medical records. The project leader and the medical monitor of the study at Bial will be informed of each withdrawal and the reason for it. To minimize the loss to follow-up, the specified patient's family member/friend (if available) will be contacted. An early discontinuation visit (EDV) (see Section 11.6.7) should be performed within 10 days, if possible, on each withdrawal. However, in case of early discontinuation due to withdrawal of consent, the patient will have the right to refuse this additional visit and phone calls and no further data will be collected for this patient apart from the reason for discontinuation. The investigator should attempt to retrieve all IMPs from all patients.

Patients may withdraw or may be withdrawn from the study for the following reasons:

- At their own request (withdrawal of consent)
- If in the investigator's opinion, for reasons of safety or ethics, continuation in the study would be detrimental to the patient's well-being
- Pregnancy
- Ineligibility/development of an exclusion criterion
- In case of an intolerable adverse event(s)
- At the specific request of the sponsor
- Lost to follow up
- Other reasons

Patients who are withdrawn are not to be replaced.

9.5 Termination of Study

9.5.1 Regular termination of study

The end of this study is defined as the date of last patient's last visit (LPLV) undergoing this study. Within 90 days of the end of a clinical study SCOPE will notify Independent Ethics Committees (IECs) and regulatory authorities about the regular termination of the study as required according to national laws and regulations. If the study has to be terminated early, this period shall be reduced to 15 days and the reasons must be clearly explained.

9.5.2 Premature termination of study

The study may be terminated prematurely for any reason and at any time by Bial, IECs, or regulatory authorities. A decision to prematurely terminate the study is binding to all investigators of all study centres. IECs and regulatory authorities will be informed about reason and time of termination according to the applicable laws and regulations.

Once dosing has begun, the study will be completed as planned unless the following criteria are satisfied that require temporary suspension or early termination of the study.

- One SAE in one patient considered at least possibly related to the IMP administration will imply an urgent benefit-risk assessment and might result in a premature study termination in favour of patients' well-being.
- New information regarding the safety of the IMP becomes available, reviewed by the DSMB, and indicating a change in the risk/benefit profile for the compound, such that the risk/benefit is no longer acceptable for patients participating in the study. The DSMB will also periodically review the safety data and is empowered to recommend modifications of the protocol (dosage levels) or temporary suspension or early termination of the study, if major concerns arise about patient safety at any time during the course of the study.
- Significant violation of Good Clinical Practice (GCP) that compromises the ability to achieve the primary study objectives or compromises patient safety.

If the study is terminated prematurely, all investigators have to inform their patients in writing and take care of appropriate follow-up and further treatment of the patients.

9.5.3 Premature termination of the study in a study centre

The sponsor reserves the right to discontinue the study at a specific study site any time. The reasons will be discussed with the principal investigator. A study site may also be discontinued

by the sponsor for major deviations from the protocol or due to difficulties experienced in running the study at that centre.

Bial may terminate this study in one particular or several study centre(s) for one of the following reasons:

- Non-compliance with GCP and/or regulatory requirements
- Centre cannot recruit an adequate number of patients
- False documentation in the eCRF due to carelessness or deliberately
- Inadequate co-operation with Bial or its representatives
- The principal investigator requests closure of his/her study centre

If the study is prematurely terminated in one (or more) study centre(s), all investigators in this study centre (in these study centres) have to inform their patients and take care of appropriate follow-up and further treatment of the patients. IEC and regulatory authorities will be informed about reason and time of termination according to the applicable laws and regulations.

10. TREATMENTS

10.1 Identity of Investigational Medicinal Product(s)

Name(s):	Zamicastat (BIA 5-1058)
Dosage form:	Tablet
Active ingredient:	Zamicastat; 1-[(3R)-6,8-difluoro-3,4-dihydro-2H-1-benzopyran-3-yl]- 1,3-dihydro-5-[2-[(phenylmethyl)amino]ethyl]-2H- imidazole-2-thione
Strength:	100 mg of zamicastat
Excipients:	Microcrystalline cellulose (Avicel PH 101 [®]), lactose 200M, povidone K-30, croscarmellose sodium, magnesium stearate, OPADRY [®] II 85F205017 blue and purified water (does not appear in the final product)
Presentation:	Blue oblong tablets, grooved on both sides, without further engravings
Pharmaceutical Manufacturer:	BIAL - Portela & C ^a , S.A., [name], [name], Portugal

A complete record of batch numbers and expiry dates of all IMP will be maintained in the TMF.

This is an open-label study. IMP will be manufactured, packed and labelled according to current Good Manufacturing Practice (GMP) and GCP guidelines, and national legal requirements.

10.2 Identity of Non-Investigational/Auxiliary Medicinal Product(s)

Not applicable

10.3 Selection of Doses in the Study

10.3.1 Selection and timing of dose for each patient

Each patient will start treatment with 50 mg zamicastat once daily (Dose A) at visit A1 and will be up-titrated step by step to the individual HTD i.e. up to 200 mg zamicastat once daily. The 100 mg tablet has to be split at the break score in two equal halves using a pill splitter.

Table 2: Dosage regimen

	Daily dose
Dose A	50 mg (half a tablet of 100 mg)
Dose B	100 mg (one tablet of 100 mg)
Dose C	150 mg (one and a half tablet of 100 mg)
Dose D	200 mg (two tablets of 100 mg)

Each next dose will start after 14 days of treatment if the previous dose was considered safe by the investigator. The up-titration is based on the following safety criteria, including but not limited to:

- Absence of symptomatic and/or clinically relevant orthostatic hypotension
- SBP > 95 mmHg or DBP > 50 mmHg
- Absence of clinically significant changes in ECG parameters (heart rate, P-R interval, QRS duration, QT and QTc interval)
- Absence of clinically significant hypersensitivity/skin allergic reactions

Patients not fulfilling the criteria for up-titration after 14 days of treatment with 50 mg zamicastat have to be withdrawn from the trial.

If the patient's next dose will not be tolerated by the patient, the dose has to be down-titrated to his/her previous dose and this dose will be considered as the individual HTD, if tolerated by the patient. Treatment at the individual HTD will be for 42 days during the maintenance period.

Zamicastat has to be taken in the morning after breakfast. The patient must not take the tablet at home on visit days (A3/B3/C3/D3, MPV1, MPV2 and MPV3).

In case a patient missed to take the dose after breakfast, (s)he should take the dose after lunch. The next dose should be taken as scheduled. If the dose was missed after lunch too, the dose for this day has to be skipped.

Patients taking 150 mg or 200 mg of zamicastat and who will not participate in the extension study will take 100 mg zamicastat for 14 days.

In case a patient will discontinue the trial early due to the occurrence of an AE, down-titration is not mandatory, but at the investigator's discretion. In case down-titration is recommended by the investigator, it should follow the same procedure as described above.

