
Methods / study design:
 
This is an open-label, multi-centre study in patients with PAH who are currently on stable treatment with at least one PAH medication. It is planned to evaluate the PK profile (24-hour profile and trough levels) and the safety, tolerability and efficacy of four different zamicastat doses. Each patient will start treatment with the lowest dose (50 mg zamicastat once daily) and the dose will be up-titrated to the individual highest tolerated dose (HTD) i.e. up to 200 mg zamicastat once daily.
 
A data safety monitoring board (DSMB) will periodically review the safety data and will issue a recommendation if the doses can be used as planned.
	

This study will consist of:

- A screening period, 5 to 12 days: visit V1
- Up to four dose finding periods, 14 days each:
 - Dose A: visits A1, A2 and A3
 - Dose B: visits B2 and B3
 - Dose C: visits C2 and C3
 - Dose D: visits D2 and D3
- Maintenance period, 42 days: visits MPV1, MPV2 and MPV3
- Follow-up period, 14 to 28 days: visits FU (down-titration) and FU

After confirmed eligibility, patients will initiate treatment with Dose A (50 mg zamicastat once daily) at visit A1 and will be treated with this dose level for 14 days. If Dose A was considered safe by the investigator, it will be up-titrated to Dose B (100 mg zamicastat once daily) at visit A3 and the patient will continue with this dosage for 14 days. Patients not tolerating Dose A have to be withdrawn from the study.

The up-titration is based on safety criteria, including but not limited to:

- Absence of symptomatic and/or clinically relevant orthostatic hypotension
- Systolic blood pressure (SBP) > 95 mmHg or diastolic blood pressure (DBP) > 50 mmHg
- Absence of clinically significant changes in electrocardiogram (ECG) parameters (heart rate, P-R interval, QRS duration, QT and QTc interval)
- Absence of clinically significant hypersensitivity/skin allergic reactions

After a positive safety evaluation at visit B3, the dose will be up-titrated to Dose C (150 mg zamicastat once daily) and the patient will continue on this dose level for a further 14 days. If Dose C was tolerated by the patient, it will be up-titrated at visit C3 to Dose D (200 mg zamicastat once daily) where the patient will remain for 56 days (14 days dose finding period + 42 days maintenance period).

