6. Stable treatment with at least one of the following approved PAH therapies for at least 90 days prior to V1: Ambrisentan, Bosentan, Macitentan, Riociguat, Selexipag, Sildenafil, Tadalafil, Epoprostenol intravenous, Iloprost inhaled or Treprostinil intravenous or subcutaneous.
7. For women: Agree not to donate ova from the time of informed consent until 30 days after the last IMP intake.
For men: Agree not to donate sperm from the time of informed consent until 90 days after the last IMP intake.

Exclusion criteria:

Patients having or being any of the following are to be excluded from the study:

1. Contraindication to zamicastat, i.e. known hypersensitivity to ingredients of zamicastat formulation.
2. Two or more consecutive measurements of SBP < 95 mmHg or DBP < 50 mmHg measured at V1.
3. Uncontrolled diabetes mellitus with HbA1c $\geq 8.5\%$ within the last three months or at screening.
4. PAH WHO Group 1 due to portal hypertension, human immunodeficiency virus (HIV) infection and schistosomiasis.
5. Any disease known to cause pulmonary hypertension other than PAH WHO Group 1.
6. Obstructive lung disease: Forced Expiratory Volume in 1 second/Forced Vital Capacity (FEV1/FVC) $< 60\%$ and FEV1 $< 60\%$ of predicted value after bronchodilator administration, as demonstrated and documented by previous spirometry data which, in

the opinion of the investigator, represent the clinical state of the patient at the time of the screening visit.

7. Restrictive lung disease: Total Lung Capacity (TLC) < 70% of predicted value, as demonstrated and documented by previous spirometry data which, in the opinion of the investigator, represent the clinical state of the patient at the time of the screening visit.
8. History of moderate to severe hepatic impairment (Child-Pugh B and C).
9. Estimated glomerular filtration rate (eGFR) < 30 mL/min/1.73 m² (measured at V1).
10. Use of the following prohibited medication or treatments during study participation: calcium channel blockers (CCBs) if used for the treatment of PAH in vasoreactive patients; drugs containing a catechol group that is metabolised by D β H e.g. rimiterole, isoprenaline, dopamine, dopexamine or dobutamide or α - and/or β -blockers.
11. Current or previous (within the past year) alcohol or substance abuse excluding caffeine or nicotine.

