6.2.1 Non-clinical aspects

Zamicastat, BIA 5-453 - a metabolite of zamicastat and its N-acetylated metabolite BIA 5-961, produced concentration-dependent decreases in DBH activity in human neuroblastoma SK-N-SH cells. In mice, zamicastat produced significant decreases in NE levels and increases in DA levels in the heart but no marked effect on NE tissue levels in the parietal and frontal cortex of the brain. Zamicastat (30 mg/kg) reduced to a similar extent the urinary excretion of NE in normotensive Wistar-Kyoto (WKY) rats and spontaneously hypertensive rats (SHR), accompanied by a significant increase in the urinary excretion of DA, and metabolites 3,4-dihydroxyphenylacetic acid (DOPAC) and homovanillic acid (HVA). The effects of zamicastat have been explored in various animal models of disease. In the SHR model, zamicastat reduced systolic and diastolic blood pressure with no changes in heart rate. In the monocrotaline (MCT) rat model of PAH, zamicastat treatment, initiated on day 12 post MCT, significantly improved the survival rate, decreased the frequency of arrhythmic beats and the number of arrhythmic episodes, and reduced the incidence of lung plexiform lesions. There was no effect on the deteriorated hemodynamics and cardiac contractility. Safety pharmacology studies demonstrated that zamicastat had no significant effects on the gross behavioural state and gastrointestinal transit in the rat. Some effects on renal function were observed at 100 or 300 mg/kg (p.o.) in the rat; small increases in urinary volume, pH and sodium excretion with a more marked effect on potassium excretion. In conscious dogs monitored by telemetry, single administration of zamicastat (20, 60 or 120 mg/kg) had no

substantial effect on arterial blood pressure, heart rate, and on the PR, QRS, QT and the QTc intervals as compared with the vehicle control animals.

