10.8.3 Other restrictions

There are no study restrictions with respect to caffeine and smoking. Grapefruits as well as foods or drinks containing grapefruit are not permitted during entire study participation (from V1 to FU).

Since zamicastat increases dopamine exposure, dopaminergic effects associated with dopaminergic therapy, such as hallucinations, nausea, dyskinesia, orthostatic hypotension and syncope, may be potentiated. Patients should be informed about the possible occurrence of such effects and cautioned against rising rapidly after sitting or lying down. Patients should be advised not to drive or operate dangerous machinery. Because of potential additive sedative effects, caution should be used when taking central nervous system (CNS) depressants.

Additional information regarding contraindications, precautions and warnings concerning zamicastat are provided in the current version of the IB. [4]

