11.3.4 Vital signs

Vital signs (systolic and diastolic blood pressure and heart rate) will be measured after the patient has rested for at least 5 minutes in supine position (first measurement) and at least one minute after the first measurement, again in supine position (second measurement). Afterwards, vital signs will be measured again in standing position after the patient has been standing for at least 3 minutes (third measurement).

At A1 and MPV3, blood pressure and heart rate will be measured before IMP intake as well as 4, 8 and 24 hours after IMP intake. Painful procedures, like drawing blood, should always be performed after vital signs measurements (not before).

Tympanic body temperature will be assessed once at all on-site visits.

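### The blood pressure criterion for raising the dose is met if either limit is cleared, so repeated low readings that would bar entry at V1 still satisfy it

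*Protocol*

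**What the plan says.** Protocol 10.3.1 raises the dose after 14 days if the investigator judges the previous dose safe. It gives an open-ended list of criteria, one of which is "SBP > 95 mmHg or DBP > 50 mmHg". The synopsis and Protocol 8.1 have the same rule, spelled out as "Systolic blood pressure (SBP) > 95 mmHg or diastolic blood pressure (DBP) > 50 mmHg", and SAP 2.5 restates it. The other listed criteria concern orthostatic hypotension, ECG changes and hypersensitivity. None of them sets a floor for resting pressure.

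At entry, exclusion criterion 2 is: "Two or more consecutive measurements of SBP < 95 mmHg or DBP < 50 mmHg measured at V1". Protocol 9.3 gives its rationale as safety.

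Protocol 11.3.4 takes two supine readings and then one standing reading at each visit. The up-titration bullet does not say which of these it applies to.

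A failure at the first step is costly: "Patients not fulfilling the criteria for up-titration after 14 days of treatment with 50 mg zamicastat have to be withdrawn from the trial". Section 9.4.2 adds: "Patients who are withdrawn are not to be replaced".

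**The concern.** The two rules share their cut-offs and, on the face of it, their purpose. The complement of excluding when either value is low is requiring that both be adequate. The up-titration bullet keeps the or, so one adequate value is enough, however low the other is.

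Blood pressure is a foreseeable signal for this drug. On the non-clinical side, "In the SHR model, zamicastat reduced systolic and diastolic blood pressure with no changes in heart rate" (Protocol 6.2.1). Protocol 10.8.3 warns that dopaminergic effects such as "orthostatic hypotension and syncope, may be potentiated". Every patient also takes at least one other PAH therapy.

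For a patient with low resting pressure but no symptoms and no postural drop, the written number gives no support for holding the dose. Deviation review would not find the case either. SAP section 6 checks the up-titration criteria as PD#24, and a patient at 85/55 has not deviated from the bullet as worded.

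**Working it through.** **Logic check.** The inputs are the two rules above.

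- Low reading, as in criterion 2: SBP < 95 or DBP < 50.
- Bullet as written: SBP > 95 or DBP > 50.
- Complement of a low reading: SBP ≥ 95 and DBP ≥ 50.

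| Reading, same on both supine measurements | Criterion 2 at V1 | Bullet as written | Complement |
|---|---|---|---|
| 85/55 | excluded | met | not met |
| 110/45 | excluded | met | not met |
| 70/51 | excluded | met | not met |
| 90/45 | excluded | not met | not met |
| 95/50 | eligible | not met | met |
| 110/70 | eligible | met | met |

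The first three rows are the gap. The 95/50 row shows a boundary mismatch the other way, because > in the bullet does not mirror < in criterion 2.

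As a check on completeness, take an integer grid (assumed: SBP 70–140, DBP 30–100, pulse pressure at least 15). It holds 1,870 low points. In 500 of these both values are low, and none meets the bullet. In the other 1,370 only one value is low, and 1,325 meet it; the remaining 45 sit on a boundary (DBP exactly 50 or SBP exactly 95). Under the complement, 0 of 1,870 pass. These are counts of grid points, not of patients.

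**How often, under assumptions.** The documents give no blood pressure distribution, so this part is illustrative. SBP and DBP are bivariate normal with patient, visit and reading components, and two supine readings are drawn at V1 and at A3. Patients who are low on both V1 readings are removed. There is no drug effect. Between-visit correlation is 0.5–0.65 and within-visit correlation 0.7–0.9. A patient is in the gap at A3 if both readings are low and both still meet the bullet. Expected patients = 32 × share.

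| Assumed mean; SD; SBP–DBP correlation | Removed at V1 | In the gap at A3 | Of 32 |
|---|---|---|---|
| 112/70; 14/9; 0.6 | 5.6–8.2% | 3.0–5.4% | 1.0–1.7 |
| 105/65; 12/8; 0.6 | 12–16% | 5.6–9.5% | 1.8–3.0 |
| 100/60; 12/8; 0.7 | 24–29% | 8–13% | 2.6–4.2 |

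For example, 32 × 0.030 = 0.96 and 32 × 0.132 = 4.2.

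**Alternative rule.** If the complement were applied to the mean of the two supine readings, the shares that pass today and would newly fail at A3 are 6.4–8.1%, 11.5–13.9% and 17.7–20.3%. That is 2.0–2.6, 3.7–4.4 and 5.7–6.5 of 32. The mean rule is also stricter than entry: readings of 93/70 and 96/70 are eligible at V1, but their mean SBP of 94.5 fails.

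**The case against.** The best case on the other side is that the bullet is only one item in a list that is openly incomplete, under a requirement that the investigator judge the previous dose safe. Orthostatic hypotension has its own bullet, the DSMB reviews safety periodically, and Protocol 9.4.2 allows withdrawal on safety grounds or when an exclusion criterion develops. All of this stands. A reader might infer that the protocol directs investigators to raise the dose in hypotensive patients. It does not, since no increase is ever compelled.

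A reader might also call the two rules contradictory. They are not. Criterion 2 is confined to V1; SAP section 6 (PD#09) shows that protocol version 2.0 lacked that limit. Up-titration is a separate decision. What remains is that one pair of limits, treated as a safety matter at entry, is applied more loosely when the dose rises, and no section requires both limits.

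The evidence that zamicastat lowers blood pressure is mixed. The fall was in hypertensive rats. Protocol 6.2.1 also reports no substantial effect on arterial pressure in conscious dogs at 20, 60 or 120 mg/kg. Section 6.2.2 reports no serious or severe adverse events, with 512 healthy subjects exposed. Section 8.2 notes that the 200 mg maximum is 6-fold below the highest multiple dose tested (1200 mg). The warning in 10.8.3 is about orthostatic effects, which the separate bullet addresses.

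Finally, the simulated shares are not a harm rate. They show ordinary variation around a threshold, with assumed inputs and no drug effect, and they do not subtract visits at which the investigator would have held the dose.

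**Conclusion.** The bullet is wrong as written. It fails only when both values are at or below their limits, whereas criterion 2 acts on either. That conclusion rests on the text alone. In practice the gap is narrow: mainly low resting pressure without symptoms or a postural drop, where only judgement stands in the way.

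The size, about 1 to 4 of 32 patients at A3, depends on the assumed distributions and correlations, on no drug effect, and on reading criterion 2 as two low supine measurements. The documents do not support the stronger inferences that such patients were in fact up-titrated, or that anyone was harmed.

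Dosing in this trial is over. SAP section 6 places the Data Review after data entry and following a database lock. The SAP revision history shows Draft 0.4 (06-JAN-2022) updated after the Data Review meeting, and SAP 3.1 cites the Data Review Report of 10-MAR-2022. A change of wording therefore cannot affect these patients.

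**What to change.** **For this trial.** Add one listing, by dose, of up-titrations at A3, B3 and C3 made when both supine readings had SBP < 95 or DBP < 50. It can be filtered from data already in Listings 16.2.4.4 (vital signs), 16.2.2.1 (drug accountability) and 16.2.2.2 (exposure and compliance). It shows whether the gap was ever used. SAP 2.5 should keep the wording of the protocol in force, and PD#24 need not be re-assessed.

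**For any later titration protocol.** Make the bullet the complement of criterion 2, in each place it appears: *SBP ≥ 95 mmHg and DBP ≥ 50 mmHg on at least one of the two supine readings; not met if both supine readings have SBP < 95 mmHg or DBP < 50 mmHg.* The ≥ mirrors the < in criterion 2. The standing reading then serves the orthostatic bullet.

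**Cost.** The listing is a small programming task. Had the reworded rule applied here, the patients in the gap would be those who newly fail: about 1 to 4 of 32 at A3 under the assumptions above. They would be withdrawn without replacement and lose the MPV3 profile. Patients failing at a later step would end at a lower dose. The supine-mean version would cost about 2 to 6.5 of 32 and is stricter than entry, so it is not preferred, although SAP 5.6.4 uses the supine mean in its summaries.
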